5.2 Analysis plan

For **Study Objective 1**, feasibility and acceptability will be evaluated using descriptive statistics of rates of eligibility, enrollment ($\geq 80\%$), attrition, reasons for refusal, and completion rates of surveys. Independent means t-tests and chi-square tests will compare

acceptors/decliners and completers/ non-completers. Web analytics (ie, Google analytics) will track logins and calculate web page access, time spent on modules, click stream data, and visitor segmentation. Aggregated and real-time access to this data will help us determine real-world use of the website so that we can make design adjustments as needed. Completion of the “action plan” module will be tallied ($\geq 70\%$ considered acceptable); factors predicting non-completion will be identified using tests of independent group differences. User engagement will be tracked for the entire study period to explore whether modules are used as a one-time resource or iteratively.

For **Study Objective 2**, for each outcome variable, we will examine the distributional qualities, extent of missing data, and satisfaction of assumptions of randomness (ie, MAR, MCAR). Descriptive statistics will evaluate sample characteristics. Covariates with significant relationships with the decisional conflict scale (DCS) will be included in final models. To obtain an effect size estimate of the decision aid in reducing decisional conflict, pairwise t-test will evaluate change in DCS mean scores from T1 to T2. A two-sided hypothesis test of the within-subject difference in adjusted means will test the null hypothesis ($H_0: \mu_1 = \mu_2$) at $\alpha = 0.05$. Rejection of the null hypothesis will indicate a significant within-subject DCS mean change from T1 to T2 ($H_1: \mu_1 > \mu_2$). Effect size estimates (Cohen’s d) will be calculated and reported. On an exploratory level, we will examine T1 to T3 and T2 to T3 mean differences to characterize the DCS trajectory. Similar procedures will analyze changes in the IPQ-R, RCACS, PROMIS Self-Efficacy, and the IES-R as secondary outcomes, controlling for key covariates. The Stage of Decision Making Scale will be assessed, and descriptive statistics will evaluate whether use of the decision aid website impacts readiness to engage in decision making, progress in making a choice, and receptivity to considering or re-considering options between timepoints T1 and T2 and between timepoints T2 and T3. The Preparation for Decision Making Scale will be assessed, and descriptive statistics will evaluate whether use of the decision aid website impacts perception of how useful a decision aid or other decision support intervention is in preparing the respondent to communicate with their practitioner at a consultation focused on making a health decision. The eHealth Impact Questionnaire-Part 2 will be assessed and descriptive statistics will evaluate the impact of using the decision aid website across three domains: 1) confidence and identification of health concerns, 2) information and presentation of website material, and 3) understanding and motivation to manage health issues.

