5.3 Sample size

The target sample size is 100.

Power Estimate: With a projected 20% attrition rate, we expect 80% power to detect an effect size of 0.3 for the T1-T2 change in DCS, with a two-sided paired t-test with a 0.05 significance level. We based this on a decision aid intervention for fertility preservation,³⁴ which reported 14% attrition and DCS means at baseline ($M = 51.6$, $SD = 32.8$) and 1-month post-intervention ($M = 16.6$, $SD = 26.5$). We assumed the same DCS baseline mean, but were conservative and assumed higher attrition, higher DCS mean at follow-up ($M = 40$, $SD = 26.5$), and correlation coefficient between measurements to be 0.3, so that the effect size will be 0.33; representing a moderate effect size based on Cohen’s taxonomy. This also follows the DCS manual.

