5.4 ClinicalTrials.gov Outcomes

Similar to endpoints, ClinicalTrials.gov outcomes are assessments that evaluate the Roadmap to Parenthood intervention. Following are the ClinicalTrials.gov outcome titles; descriptions, and timeframes.

Outcome 1 (Primary)

Title: Decisional Conflict Scale (DCS)

Description: The Decisional Conflict Scale (DCS) is a validated survey that assesses personal uncertainty in making healthcare decisions; modifiable factors contributing to uncertainty; and the quality of the decision made. It is reliable and responsive to change, and the most widely used measure of decision-making quality. The survey has 16 questions, with responses on a 5-point scale ranging from “strongly agree” (1) to “strongly disagree” (5). Total scores range from 16 to 80, with higher scores indicating greater uncertainty (worse outcome). The outcome will be reported as the mean difference from baseline to 1 and 3 months, with standard deviation.

Timeframe: 3 months

Outcome 2 (Secondary)

Title: Unmet Fertility Information

Description: This investigator-designed survey assesses perceived information needs about fertility topics such as the risk of infertility; risk of early menopause; options to assess fertility status; options to preserve fertility; and options for alternative family-building. The survey has 5 questions, each answered by a Yes / No response. Yes is scored as 1, and no is scored as 0. Total scores range from 0 to 5, with higher scores indicating greater perceived knowledge. The outcome will be reported as the mean difference from baseline to 1 and 3 months, with standard deviation.

Timeframe: 3 months

Outcome 3 (Secondary)

Title: Illness Perceptions Questionnaire-Revised (IPQ-R)

Description: The Illness Perceptions Questionnaire-Revised (IPQ-R) is a survey that assesses cognitive and emotional representations of illness and is validated in cancer populations. The survey has 28 questions, answered on a 5-point scale ranging from “strongly disagree” (1) to “strongly agree” (5). Total scores range from 28 to 140, with higher scores indicating worse outcomes. The outcome will be reported as the mean difference from baseline to 1 and 3 months, with standard deviation.

Timeframe: 3 months

Outcome 4 (Secondary)

Title: Reproductive Concerns After Cancer (RCAC) Scale

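### Section 5.2 describes the primary DCS analysis both as an unadjusted paired t-test and as an unnamed adjusted model, and as written it uses only complete T1-T2 pairs despite 20% projected attrition

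*Combined protocol and SAP*

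**What the plan says.** **The test.** Section 5.2 (Study Objective 2) says that, for the primary outcome, a "pairwise t-test will evaluate change in DCS mean scores from T1 to T2". The next sentence reads: "A two-sided hypothesis test of the within-subject difference in adjusted means will test the null hypothesis". Just before both: "Covariates with significant relationships with the decisional conflict scale (DCS) will be included in final models". The type of model, the DCS visit used for the screen and the threshold are not given. The test is two-sided at 0.05, but the alternative is written as mu1 > mu2. Secondary outcomes follow similar procedures, with control for key covariates.

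**Sections that bear on it.** Section 5.3 computes power "with a two-sided paired t-test with a 0.05 significance level". Section 5.4 says of the DCS: "The outcome will be reported as the mean difference from baseline to 1 and 3 months, with standard deviation". Neither mentions adjustment.

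**Covariates.** Section 4.0 first names sociodemographic and medical characteristics, uncertainty management preference, financial well-being and health literacy as a priori covariates and process variables. Its later paragraph on Objective 2 leaves financial well-being off the covariate list and speaks of tracking change in the financial measures. The table in Section 5.1 puts both financial scales under covariates, collected at T1, T2 and T3. Appendix B marks them at T1 only.

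**Missing data.** Section 5.3 states: "With a projected 20% attrition rate, we expect 80% power to detect an effect size of 0.3". Section 4.0 provides for reminders and staff follow-up. Section 5.2 will compare "acceptors/decliners and completers/ non-completers" and examine the "extent of missing data, and satisfaction of assumptions of randomness (ie, MAR, MCAR"). No section says how a missing T2 score is then handled in the primary analysis.

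**The concern.** Objective 2 exists to produce preliminary effect sizes, so the reported change and its Cohen's d are what the pilot delivers. One analyst following Section 5.2 could report a plain paired change. Another could report a model-adjusted difference with covariates picked from the data. Both would be within the text.

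With covariates measured once at T1 and mean-centred, the point estimate of change would be the same, although the standard error, and a d built on the residual SD, could differ. The financial scales may be collected at every visit. If they entered as time-varying covariates, the adjusted change could itself differ from the unadjusted one.

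The second issue is who contributes. A paired t-test drops everyone without a T2 score. Their T1 scores, and any T3 scores, then do not inform the primary contrast, and the estimate moves if drop-outs and completers differ at baseline.

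**Working it through.** **Inputs (Section 5.3).** T1 mean 51.6, SD 32.8; assumed T2 mean 40, SD 26.5; correlation 0.3; 100 enrolled; 20% attrition, hence 80 pairs.

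**1. The plan's effect size.**
- Change = 51.6 - 40 = 11.6.
- SD of change = sqrt(32.8² + 26.5² - 2 × 0.3 × 32.8 × 26.5) = sqrt(1256.57) = 35.45.
- d = 11.6 / 35.45 = 0.327, which is the plan's 0.33.
- Other denominators do not give 0.33: baseline SD, 11.6 / 32.8 = 0.35; pooled SD, 0.39; residual SD after adjusting for baseline DCS, 11.6 / (26.5 × sqrt(1 - 0.3²)) = 11.6 / 25.28 = 0.46.

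So Section 5.3 implies the unadjusted change divided by its own SD.

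**2. What adjustment could do.** In a regression of change on mean-centred T1 covariates, the intercept equals the plain mean change. The estimate stays at 11.6, but d need not. If covariates explain a share R² of the variance of change (assumed) and d uses the residual SD, then d = 0.327 / sqrt(1 - R²) = 0.34, 0.37 and 0.39 for R² of 0.1, 0.2 and 0.3. The invariance does not extend to covariates that change between visits.

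**3. Precision when drop-out is uninformative.**
- Complete pairs: SE = 35.45 / sqrt(80) = 3.96.
- Slope of T2 on T1: b = 0.3 × 26.5 / 32.8 = 0.242.
- T1 from all 100 and T2 from 80: SE = sqrt((1 - b)² × 32.8² / 100 + 26.5² × (1 - 0.3²) / 80) = sqrt(14.16) = 3.76.
- Equivalent complete pairs: 35.45² / 14.16 = 88.7. For correlations of 0.1, 0.5 and 0.7 the figure is 90.2, 87.3 and 86.2.

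**4. Shift when drop-out depends on baseline DCS.** Shift in the complete-pairs change = (1 - b) × 0.20 × gap, where the gap is the assumed difference in mean T1 score between drop-outs and completers.

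| Assumed gap | Shift in change |
|---|---|
| 5 points | 0.8 |
| 10 points | 1.5 |
| 20 points | 3.0 |

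At 10 points the shift is 1.52 / 3.96 = 0.38 SE, and d becomes (11.6 - 1.52) / 35.45 = 0.28 or (11.6 + 1.52) / 35.45 = 0.37, depending on the sign of the gap.

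**5. Drop-outs who improve less.** Suppose completers improve by 11.6 and those missing T2 by a fraction f of that. Whole-sample change = 11.6 × (0.8 + 0.2f): 10.4 at f = 0.5 and 9.3 at f = 0. Divided by 35.45, d is 0.29 and 0.26.

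**6. Simulation check.** Assumed settings: 100 participants, about 20% missing T2, half of these returning at T3, T2-T3 correlation 0.6, T3 mean 40. The three-visit model was fitted by maximum likelihood, and the true change was 11.6.

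| Drop-out depends on | Complete pairs | Model |
|---|---|---|
| Baseline DCS (log-odds ±0.3 per SD) | 10.2 / 13.1 | 11.6 / 11.6 |
| Unobserved change | 9.4 / 13.6 | 10.7 / 12.3 |

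The model removes the first bias. About 40% of the second remains, or about 50% if nobody returns at T3.

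**The case against.** The best defence is that the documents already point one way. Sections 5.3 and 5.4 fit the unadjusted change, and only one form of d gives 0.33. That stands, and it makes the conflict easy to resolve. It does not remove it: Section 5.2 is where the test is defined, and its carry-over to secondary outcomes with control for covariates suggests that adjustment was meant.

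A second defence is scale. At 80 pairs the 95% half-width is about 7.9 points, or about 0.22 in d, so every d from 0.26 to 0.39 in steps 2, 4 and 5 lies inside that interval around 0.33. The drop-out gap and the R² values are assumptions. This also stands, and it is why the point is modest.

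A third is that a mixed model goes further than the conflict requires. Deleting the adjustment and stating the analysis set would settle the wording, but would leave the 20% without T2 out of the primary contrast.

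A reader might infer more than the documents support:
- **That the significance screen biases the result.** This is not shown. Nor is it shown to be harmless, because Sections 4.0 and 5.1 admit financial covariates that may be measured repeatedly.
- **That missing data are ignored, or that T1 and T3 scores of those missing T2 are wasted.** Follow-up and diagnostics are planned. Those scores can enter the completer comparison and the exploratory T1-T3 change. They are absent only from the primary contrast.
- **That the mixed model restores the stated 80% power.** At d = 0.3, power is 75.5% with 80 pairs and about 79.8% with an effective 88.7. But 80 pairs give 83.0% at 0.33, and the smallest effect detectable with 80% power is 0.317, which rounds to 0.3. The near match is incidental and does not correct Section 5.3.

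**Conclusion.** The point holds. Section 5.2 gives two incompatible descriptions of the primary test, leaves the adjusted model unnamed with covariates chosen from the data, and writes a directional alternative for a two-sided test. The primary contrast, as the stated t-test would compute it, rests on complete pairs, with no other rule for missing T2 scores.

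The numerical consequence is modest: 3.96 against 3.76 in standard error if drop-out is uninformative, and about 1.5 points of bias per assumed 10-point baseline gap, in a direction that cannot be known beforehand. The precision figures rest on the plan's own SDs, correlation and attrition. The bias figures rest on assumed differences between drop-outs and completers. For a pilot whose product is an effect size, the greater risk is that the reported d depends on choices made after the data are seen.

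**What to change.** Replace the primary-test sentences in Section 5.2 with one analysis:

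> The primary analysis is an unadjusted linear mixed model of DCS (REML) in all participants with a T1 score, with visit (T1, T2, T3) as a factor and unstructured covariance. The primary estimate is the T1-T2 contrast with 95% CI, tested two-sided at 0.05 against mu1 ≠ mu2. Cohen's d is this contrast divided by the SD of the T1-T2 change.

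Then:
- Remove the adjusted means and the significance screen from the primary test.
- Make any adjusted analysis secondary. Name its covariates in advance from the lists in Section 4.0, including financial well-being, use T1 values only, and mean-centre them.
- Reword the carry-over to secondary outcomes so that it matches.
- Reconcile the Section 5.1 table with Appendix B on when the financial scales are collected.
- Keep the unadjusted paired t-test, which Section 5.3 powers, as a sensitivity analysis. Add one in which those missing T2 show half or none of the improvement.

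The cost is SAP wording and a few lines of syntax in SPSS, which Section 6.1 already names, with no new data. The price is slightly more analysis work and reliance on data missing at random. That assumption does not remove bias from drop-out that depends on unobserved change; the half-or-none analysis probes it.

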5.3 Sample size

The target sample size is 100.

Power Estimate: With a projected 20% attrition rate, we expect 80% power to detect an effect size of 0.3 for the T1-T2 change in DCS, with a two-sided paired t-test with a 0.05 significance level. We based this on a decision aid intervention for fertility preservation,³⁴ which reported 14% attrition and DCS means at baseline ($M = 51.6$, $SD = 32.8$) and 1-month post-intervention ($M = 16.6$, $SD = 26.5$). We assumed the same DCS baseline mean, but were conservative and assumed higher attrition, higher DCS mean at follow-up ($M = 40$, $SD = 26.5$), and correlation coefficient between measurements to be 0.3, so that the effect size will be 0.33; representing a moderate effect size based on Cohen’s taxonomy. This also follows the DCS manual.

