1.0 SPECIFIC STUDY AIMS

Many young adult female (YA-F) cancer survivors (18-39 years old) who received gonadotoxic therapy will experience fertility problems when trying to build a family. After cancer, having a child will often require assisted reproductive technology (ART), surrogacy, or adoption. However, there are significant informational, psychosocial, and financial barriers to ART and adoption. Lack of awareness, unrealistic expectations, distress, and avoidance or postponement of fertility care put YA-Fs at-risk for being unable to have a child when they are ready or experiencing greater difficulty, distress, and higher costs during the process.

The overall goal of this work is to pilot test a single-arm intervention of a decision aid tool (interactive website identified as the “Roadmap to Parenthood”) to assist young adult female cancer survivors in making decisions and preparing for family-building after cancer.

Study Objective 1: Examine feasibility and acceptability of a decision aid intervention in a single-arm pilot trial.

Study Objective 2: Obtain preliminary effect sizes of the decision aid intervention using a pre-post test design.

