3.3 Enrollment

The target sample size is 100.

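### Section 5.3 claims 80% power at an effect size of 0.3, but 80 pairs give about 76%; 80% is reached at 0.317 (minor wording correction)

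*Combined protocol and SAP*

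**What the plan says.** Section 3.3 sets enrolment: "The target sample size is 100". Section 5.3 repeats that target and makes the plan's only power statement: "With a projected 20% attrition rate, we expect 80% power to detect an effect size of 0.3 for the T1-T2 change in DCS". It names the test as a paired t-test, two-sided, at the 0.05 level. Section 5.2 also plans a two-sided test at 0.05 for the T1-T2 change in DCS: "A two-sided hypothesis test of the within-subject difference in adjusted means".

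Section 5.3 then derives an effect size. It takes a baseline mean of 51.6 (SD 32.8) from an earlier fertility decision-aid study, assumes a follow-up mean of 40 (SD 26.5), and sets the "correlation coefficient between measurements to be 0.3, so that the effect size will be 0.33".

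The paragraph therefore carries two effect sizes. The 80% power is attached to 0.3. No power is given for 0.33.

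**The concern.** Every input to the power figure is stated, so the figure can be checked directly, and it does not come out. Read literally, the design has less than 80% power at the effect named. The paragraph also leaves unclear which effect the trial is sized for, and this matters because 100 enrolled is enough for 0.33 but not for 0.30.

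Little is at stake for this trial. It is a single-arm pilot whose second objective is to "Obtain preliminary effect sizes of the decision aid intervention using a pre-post test design", and no go/no-go rule uses the power figure. The practical risk is reuse: a later study sized on 80 completers for 80% power at 0.3 would fall short of the 90 completers that effect requires.

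**Working it through.** **Inputs (all from Section 5.3; enrolment also in 3.3, sidedness and alpha also in 5.2).** Enrolled 100; attrition 20%; two-sided paired t-test, alpha 0.05; stated effect 0.3; means 51.6 and 40; SDs 32.8 and 26.5; correlation 0.3.

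**Step 1. Evaluable pairs.** 100 × (1 − 0.20) = 80, so df = 79.

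**Step 2. Reproduce the plan's own effect size.**
- Variance of change = 32.8² + 26.5² − 2 × 0.3 × 32.8 × 26.5 = 1075.84 + 702.25 − 521.52 = 1256.57.
- SD of change = √1256.57 = 35.45.
- d = (51.6 − 40) / 35.45 = 11.6 / 35.45 = 0.327.

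This rounds to the stated 0.33, so that figure is confirmed.

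**Step 3. Power with 80 pairs.** Exact power comes from the noncentral t distribution with 79 df and noncentrality d × √80:

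| Standardized change d | DCS points (d × 35.45) | Power |
|---|---|---|
| 0.30 | 10.6 | 75.5% |
| 0.317 | 11.2 | 80.0% |
| 0.327 (plan's scenario, unrounded) | 11.6 | 82.4% |
| 0.33 (as printed) | 11.7 | 83.0% |

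Simulation with 200,000 runs agrees: 75.7% at 0.30, 80.0% at 0.317 and 82.4% at 0.327. The shortfall at 0.30 is 80 − 75.5 = 4.5 percentage points.

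**Step 4. Could another calculation give 80% at 0.30?**
- Normal approximation, 80 pairs: Φ(0.30 × √80 − 1.96) = Φ(0.723) = 76.5%.
- One-sided 0.05, 80 pairs (tried because 5.2 writes its alternative hypothesis as directional): 84.5%.
- No attrition, 100 pairs, two-sided: 84.4%.
- 14% attrition, the earlier study's rate, 86 pairs, two-sided: 78.5% exact, 79.4% by normal approximation.

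The last is closest, but the section deliberately projects a higher attrition than 14%. Nothing that keeps the stated inputs gives 80%.

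**Step 5. Numbers needed for 80% power.**
- At d = 0.30: 90 completers; 90 / 0.8 = 112.5, so 113 enrolled.
- At d = 0.327: 76 completers; 76 / 0.8 = 95 enrolled.
- At d = 0.33: 75 completers; 75 / 0.8 = 93.75, so 94 enrolled.

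**Step 6. Dependence on the assumed correlation.** Same means and SDs, 80 pairs. The values other than 0.3 are my assumptions:

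| Correlation | d | Power |
|---|---|---|
| 0.10 | 0.290 | 72.5% |
| 0.20 | 0.307 | 77.3% |
| 0.25 | 0.316 | 79.8% |
| 0.30 (plan) | 0.327 | 82.4% |
| 0.35 | 0.339 | 85.0% |

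**The case against.** The strongest reply is rounding. The detectable effect of 0.317 is 0.3 to one decimal, so at its printed precision the sentence is correct, and 75.5% arises only if 0.3 is read as 0.300. The plan also gives no reason to target exactly 0.300. The one scenario it derives has more than 80% power, and nothing operational changes.

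Much of this stands. Rounding is the likeliest source, and it is a reason to treat the point as a correction of wording rather than a design flaw. It does not make the sentence adequate. The paragraph gives its other effect size to two decimals, so a reader will take 0.3 as a separate value. One decimal is also too coarse for a power statement: with 80 pairs, power is 59.8% at 0.25 and 86.9% at 0.349, and both effects print as 0.3.

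A second fair objection is that calling the sample size adequate depends on an assumed correlation. That is right, and the verdict is worded accordingly.

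**Conclusion.** The concern holds, and it is minor. With 80 pairs and the stated test, power at 0.30 is 75.5%, not 80%; 80% power corresponds to 0.317. The sample size of 100 is adequate for the scenario the plan derives (11.6 points, d = 0.327, 82.4% power), given 20% attrition and a correlation of 0.3. The margin is thin: at a correlation of 0.25, power is already just under 80%. If exactly 0.30 were the effect of interest, 100 would not be enough.

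These figures are for the unadjusted paired t-test named in 5.3. The effect on any covariate-adjusted analysis under 5.2 was not assessed.

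**What to change.** Replace the power sentence in Section 5.3 with wording such as: *Enrolling 100 with 20% attrition leaves 80 evaluable pairs, which gives 80% power for a standardized change of 0.317 (about 11.2 DCS points) and 82% power for the assumed 11.6-point change (d = 0.327), using a two-sided paired t-test at 0.05.* If 0.30 is kept, give its power as 76%. Two decimals (0.32 and 0.33) would also serve, provided each effect is paired with its own power: 80.7% at 0.32 and 83.0% at 0.33.

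The cost is one reworded sentence, with no change to enrolment, test or analysis.
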